11.1.4. Tables

Table 14.2.2.1: MOR106 serum concentrations ($\mu\text{g/mL}$): Individual data and descriptive statistics and time point

Subject data and descriptive statistics per analysis visit/time point of the serum concentrations will be displayed.

Population: PK analysis set.

11.1.5. Figures

Figure 14.2.2.5: MOR106 trough serum concentrations ($\mu\text{g/mL}$): Subject profile plots (linear-linear scale)

Subject profile plots of the MOR106 trough serum concentrations over time with all subjects on the same plot (up to Day 57 including only pre-dose timepoints and Day 57 results to be displayed on the same plot).

Population: PK analysis set.

Figure 14.2.2.6: MOR106 trough serum concentrations ($\mu\text{g/mL}$): Mean (\pm SE) concentration over time (linear-linear scale)

Arithmetic mean with SE of the MOR106 trough serum concentrations over time (up to Day 57 including only pre-dose timepoints and Day 57 results to be displayed on the same plot).

Population: PK analysis set.

11.1.6. Listings

Listing 16.2.7.1: PK data handling

Listing per treatment, subject and analysis visit/time point of any data issue.

Population: PK analysis set.

Listing 16.2.7.2: Actual PK blood sampling times (h)

Listing per treatment, subject and analysis visit/time point of the PK sampling times relative to the actual drug intake. Deviations from the scheduled sampling times of more than 10% will be flagged (for post-dose assessments), as well as pre-dose samples that were actually taken post-dosing.

Population: PK analysis set.

Listing 16.2.7.3: MOR106 serum concentrations ($\mu\text{g/mL}$): Individual data

Listing per treatment, subject and analysis visit/time point of all MOR106 serum concentration data.

Population: PK analysis set.

12. ANALYSIS OF IMMUNOGENICITY AND DEFINITION OF ANALYSIS TLFS

Table 14.2.3.1: Anti-MOR106 antibodies (ADA): Tabulation per treatment and time point

Frequency table of ADA status (positive/negative) and potential drug interference in the assay when ADA negative (yes/no) by treatment group at Day 1 and all post-dose time points.

Population: safety analysis set.

Listing 16.2.8.1: Anti-MOR106 antibodies (ADA): Full listing

Listing per treatment, subject and analysis visit/time point of ADA results, titer and potential drug interference.

Population: safety analysis set.

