4.2.2. Clinical Study Design Rationale

A placebo-controlled design is used to account for the high placebo effect that can be observed in the given population. The overall treatment period of 8 weeks is proposed to allow for a thorough investigation of the safety profile over a time period where already significant clinical treatment effects of both antibodies can be expected. A follow-up period of 16 weeks is selected to further monitor any MOR106 induced clinical effects and to observe any potential ADA development after treatment stop.

The clinician and subject-rated scales selected for this study are based on recommendations made by the Harmonising Outcome Measures for Eczema (HOME) trials group (Spuls, Gerbens, & Simpson, 2017) (Schmitt, Spuls, & Thomas, 2014). They are established scales recognized in this field.

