7.3.7. Analysis of Immunogenicity Data

ADA status (positive/negative), titer (when ADA status was positive), and potential drug interference in the assay when ADA negative (yes/no) will be summarized descriptively for each part of the study, by treatment group, and time point.

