2.3.2. Secondary Endpoints

The secondary endpoints are:

- MOR106 serum concentrations after repeated s.c. administrations from baseline through Day 169/ED visit.
- Occurrence of ADA from baseline through Day 169/ED visit.

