|--------------------------|------------|----------------------|----------------------|
| Baseline ^[1] | 1 | -INF | 1 |
| Day 15 | 15 | 2 | 22 |
| Day 29 | 29 | 23 | 36 |
| Day 43 | 43 | 37 | 50 |
| Day 57 | 57 | 51 | 64 |
| Day 71 | 71 | 65 | 85 |
| Day 99 | 99 | 86 | 113 |
| Day 127 | 127 | 114 | 141 |
| Day 155 | 155 | 142 | 162 |
| Day 169 | 169 | 163 | 176 |
| > Day 169 ^[2] | NA | 177 | +INF |

[1] Baseline will be defined as the last measurement before the start of IMP.
[2] This time point will be only listed.

Time windows for pregnancy test:

| Time point label | Target day | Interval lower bound | Interval upper bound |
|--------------------------|------------|----------------------|----------------------|
| Baseline ^[1] | 1 | -INF | 1 |
| Day 29 | 29 | 2 | 43 |
| Day 57 | 57 | 44 | 85 |
| Day 113 | 113 | 86 | 141 |
| Day 169 | 169 | 141 | 176 |
| > Day 169 ^[2] | NA | 177 | +INF |

[1] Baseline will be defined as the last measurement before the start of IMP.
[2] This time point will be only listed.

Time windows for [REDACTED]

| Time point label | Target day | Interval lower bound | Interval upper bound |
|-------------------------|------------|----------------------|----------------------|
| Baseline ^[1] | 1 | -INF | 1 |
| Day 57 | 57 | 2 | 64 |
| > Day 57 ^[2] | NA | 65 | +INF |

[1] Baseline will be defined as the last measurement before the start of IMP.
[2] This time point will be only listed.

Time windows for immunogenicity (ADA), PD and biomarkers:

| Time point label | Target day | Interval lower bound | Interval upper bound |
|--------------------------|------------|----------------------|----------------------|
| Baseline ^[1] | 1 | -INF | 1 |
| Day 29 | 29 | 2 | 43 |
| Day 57 | 57 | 44 | 71 |
| Day 85 | 85 | 72 | 99 |
| Day 113 | 113 | 100 | 127 |
| Day 141 | 141 | 128 | 155 |
| Day 169 | 169 | 156 | 176 |
| > Day 169 ^[2] | NA | 177 | +INF |

[1] Baseline will be defined as the last measurement before the start of IMP.
[2] This time point will be only listed.

Time windows for injection site reactions:

| Time point label | Target day | Interval lower bound | Interval upper bound |
|-------------------------|------------|----------------------|----------------------|
| Day 1 | 1 | 1 | 1 |
| Day 4 | 4 | 2 | 10 |
| Day 15 | 15 | 11 | 22 |
| Day 29 | 29 | 23 | 36 |
| Day 43 | 43 | 37 | 50 |
| Day 57 | 57 | 51 | 64 |
| Day > 57 ^[1] | NA | 65 | +INF |

[1] This time point will be only listed.

Time windows for skin swab:

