8.1.6. Analysis of Immunogenicity Data

ADA status (positive/negative), ADA titer when ADA positive and potential drug interference in the assay when ADA negative (yes/no) will be listed by treatment group and time point. ADA status and potential drug interference will be also summarized.

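### ADA status is tabulated only visit by visit, so no subject-level occurrence is pre-specified for a secondary endpoint that runs from baseline to Day 169

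*SAP*

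**What the plan says.** The endpoint is worded alike in Protocol 4.3.2 and SAP 2.3.2: "Occurrence of ADA from baseline through Day 169/ED visit". Protocol 4.2.2 gives, as one reason for the 16-week follow-up, "to observe any potential ADA development after treatment stop".

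SAP section 12 plans two outputs:

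- Table 14.2.3.1, "Anti-MOR106 antibodies (ADA): Tabulation per treatment and time point", described as a "Frequency table of ADA status (positive/negative) and potential drug interference in the assay when ADA negative (yes/no) by treatment group", with Day 1 and each later time point shown.
- Listing 16.2.8.1, described as "Listing per treatment, subject and analysis visit/time point of ADA results, titer and potential drug interference".

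SAP 8.1.6 adds only that "ADA status and potential drug interference will be also summarized". Protocol 7.3.7 planned that status, titer and interference "will be summarized descriptively for each part of the study, by treatment group, and time point". The SAP keeps status and interference in the table and moves titer to the listing.

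Three general SAP rules decide what reaches the table:

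- Section 5.2 ("Time windows for immunogenicity (ADA), PD and biomarkers") sets a baseline window and six later ones, for Days 29, 57, 85, 113, 141 and 169. Results from Day 177 on are only listed.
- Section 5.3 keeps one record per post-baseline window, the one nearest the target day.
- Section 7.6 counts only non-missing values in a percentage's denominator. It also names the treatment group size as the default, which may be restricted.

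No readable text in either document defines an ever-positive or treatment-emergent ADA subject, a denominator for such a status, or a rule for subjects positive at baseline.

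**The concern.** The endpoint describes a period, while the table describes a series of separate days. A reader of the study report will want to know how many subjects in each arm had ADA at any time after dosing, and how many of those were negative beforehand. No planned summary answers that.

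The pattern that visit rows handle worst has already been seen with this product. Protocol 4.4 reports two ADA cases from the first-in-human study: one transient case in a healthy subject, and one subject with atopic dermatitis who turned positive during follow-up, with an effect on PK. Transient and late-onset cases scatter across visit rows.

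The SAP already uses the missing logic elsewhere. For laboratory, ECG and vital-signs data it derives a worst post-baseline status per subject from all records, including unscheduled and follow-up visits (14.3.8, the worst-case section under 14.4, 14.5.6). It also applies a treatment-emergent rule against baseline (14.3.7, 14.4.6, 14.5.5). ADA occurrence is a named secondary endpoint and gets neither.

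If the count is left to be made from the listing, the handling of baseline positives, missed samples and possible interference will be settled after the data are seen.

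**Working it through.** **No plan figure to reproduce.** Neither document states an ADA rate. The one probability in Protocol 7.1 concerns adverse events (1 − 0.95^40 = 87.1%, against the stated 87%) and plays no part here.

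**Inputs.** 40 subjects on MOR106 (Protocol 7.1). Six post-baseline ADA visits (SAP 5.2 and the Schedule of Activities). Protocol 6.6 speaks of 8 ADA samples, while the schedule marks 7 visits (Day 1 plus six); I use the schedule. The positive counts below are assumed, and every subject is assumed to be sampled at every visit.

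**Step 1: what visit rows leave open.** Suppose k of 40 subjects are positive at each of six visits. If they are the same subjects each time, the number ever positive is k. If they are different subjects each time, it is min(40, 6k). Every whole number between is possible. The intervals are Clopper-Pearson: for x of n, the lower limit is the 2.5% quantile of Beta(x, n − x + 1) and the upper limit is the 97.5% quantile of Beta(x + 1, n − x).

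| Positive at every visit | Fewest ever positive (95% CI) | Most ever positive (95% CI) |
|---|---|---|
| 1/40 = 2.5% | 1/40 = 2.5% (0.1% to 13.2%) | 6/40 = 15.0% (5.7% to 29.8%) |
| 2/40 = 5.0% | 2/40 = 5.0% (0.6% to 16.9%) | 12/40 = 30.0% (16.6% to 46.5%) |
| 3/40 = 7.5% | 3/40 = 7.5% (1.6% to 20.4%) | 18/40 = 45.0% (29.3% to 61.5%) |

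Within each line, Table 14.2.3.1 would look identical at both extremes.

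**Step 2: a visit row can lose a positive.** Take a subject who is negative at the scheduled Day 57 visit and positive on an unscheduled sample on Day 64. Both fall in the Day 57 window (Days 44 to 71). The distances from target are 0 and 7 days, so the negative record is kept and the positive one does not enter the table.

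**Step 3: a visit percentage can also exceed subject-level occurrence.**

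- *Shrinking denominator.* Assume 2 of 40 subjects are persistently positive and 20 negative subjects have left by Day 169. With the non-missing denominator the Day 169 row shows 2/20 = 10%, while 2/40 = 5% were ever positive. If the group size were used as denominator instead, this effect would vanish.
- *Baseline positives.* Assume 2 subjects are positive on Day 1 and stay positive, and nobody converts. Every row shows 2/40 = 5%, while the number newly positive is 0.

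**Step 4: what the table does show.** Day 1 status has its own row, so the number positive at baseline in each arm is visible. Possible interference among negatives is shown at each visit. Missing are the cross-classification of baseline against later status and the roll-up of both items to the subject.

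**The case against.** Several points on the other side have force.

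- **The data are not lost.** Listing 16.2.8.1 holds status, titer and interference by subject and visit, for at most 60 subjects. A reader might infer that ADA occurrence becomes unknowable. It does not: ever-positive subjects can be counted. What is absent is a pre-specified rule, denominator and tabulated figure.
- **The SAP did not drop a planned analysis.** Protocol 7.3.7 was already by time point. For status and interference the SAP follows it, so the gap lies in both documents.
- **The cumulative reading is an interpretation.** The endpoint text does not speak of subjects, and the objective is to monitor ADA. Still, a period from baseline to Day 169 is not described by any single visit row.
- **Timing matters too.** The follow-up rationale asks about ADA after treatment stops, which visit rows answer well. That is a reason to keep them; it does not make them a measure of occurrence.
- **Interference and baseline positivity are not ignored.** A reader might infer that unreadable negatives are silently counted as negative. The table shows interference among negatives at each visit; only the subject-level category is missing.
- **The stakes are lower, and part of the plan is hidden.** SAP section 1 says development in atopic dermatitis was stopped for futility. Some change bullets in SAP 8.2.1 are redacted, and the table layouts sit in a separate mock document (SAP 7.9.3). A subject-level row there cannot be excluded. The readable bullets do not mention ADA, and the SAP ties the adaptation for early termination to efficacy and pharmacodynamics.

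**Conclusion.** The point holds as a gap in pre-specification: a period-long secondary endpoint has only a visit-by-visit summary, and visit percentages do not determine how many subjects had ADA.

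Its possible size depends on the data. With 1/40 positive at each of six visits, subject-level occurrence may be anywhere from 2.5% to 15%. This rests on assumed counts and complete sampling. The 15% is the upper extreme, reached only if six different subjects are each positive once; it is not an expected value.

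A reader might also infer that the visit table always understates occurrence. The documents do not support that. Scattered positives and the one-record rule push visit rows below subject-level occurrence. Shrinking denominators push them above it, and persistent baseline positives push them above new occurrence. The direction cannot be known in advance.

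The change is worth making because it costs almost nothing and gives the endpoint an estimate that matches its wording.

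**What to change.** Add a subject-level block to Table 14.2.3.1, by treatment group. Use all post-baseline samples, unscheduled ones included. Take as denominator the subjects with at least one post-baseline ADA result:

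- (a) positive at any post-baseline time;
- (b) negative at baseline and positive later, with subjects positive at baseline shown on a separate line. A titer-boost category belongs here only if the assay's threshold is stated beforehand, since the documents give none;
- (c) never positive, with at least one post-baseline negative flagged for possible drug interference.

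An exact 95% CI is optional, because the planned ADA analysis is descriptive. Keep the per-visit rows to show timing. State the derivation in SAP 8.1.6 and the change in 8.2.1. If the database is already locked, 8.2.2 provides for recording it with a justification in the study report.

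The cost is one derivation and a few table rows. Status, titer and interference flag are already collected, so no new sample or visit is needed.

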13. ANALYSIS OF PHARMACODYNAMICS AND DEFINITION OF ANALYSIS TLFS

13.1.1. Disease Status Definition

[REDACTED]

13.1.2. Tables

No table will be provided for these parameters.

13.1.3. Figures

No figure will be provided for these parameters.

13.1.4. Listings

Listing 16.2.9.3:

[REDACTED]

Population: safety analysis set.

14. ANALYSIS OF SAFETY AND DEFINITION OF ANALYSIS TLFS

The analysis of safety data will be descriptive. No inferential statistics will be computed.

The analysis of safety assessments in this study will include summaries of the following categories of safety and tolerability data collected for each subject (safety analysis set):

- Adverse events
- Non-drug related therapies
- Laboratory safety
- Electrocardiogram (ECG) investigations
- Vital signs
- Physical examination

14.1. ADVERSE EVENTS

14.1.1. Coding of Reported Terms

All adverse event terms are expected to be coded using the MedDRA coding dictionary (version 21.0 or higher).

All tables in this section will show the AE terms coded into preferred terms and system organ classes. Subject listings will also show the reported terms. All other coding levels will only be shown in a listing summarizing coding or when explicitly mentioned.

14.1.2. Definition of Treatment-emergent Adverse Events

All adverse events starting as of the point of administration of study drug (i.e. start date of dose administration for s.c. dosing) until the last contact of the subject are defined as treatment-emergent adverse events (TEAE).

All adverse events tables will only show TEAEs.

Adverse events starting before administration of study drug (not TEAEs) will only be listed.

If an AE starts before administration of study drug but worsens after then:

- Until the worsening, the AE will be considered as a non-TEAE;
- From the worsening, the AE will be considered as a TEAE.

But if an AE starts before administration of study drug and improves after the first dose, the AE will not be considered as a TEAE.

14.1.2.1. Combining of Events to be Able to Count Number of Events

A worsening is defined when one of the attributes of the events worsens (severity, seriousness, relationship or action taken). Worsenings observed after first dose of study medication of an event will be considered as a new event, improvements will not.

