7.3.8.2. Adverse Events

Clinical and laboratory AEs will be coded using the latest version of the Medical Dictionary for Regulatory Activities. System Organ Class (SOC), High Level Group Term, High Level Term, Preferred Term, and Lower-Level Term will be attached to the clinical database.

Treatment-emergent adverse events (TEAEs) are defined as those with an onset date/time on or after the start date/time of the first IMP administration (including the follow-up period). Additionally, analyses will also be created, restricted to events with an onset date on or after the IMP start and up to 30 days after last dose of IMP.

Summaries (number and percentage of subjects) of TEAEs per subject by SOC and Preferred Term will be provided by treatment group. TEAEs will also be summarized by causal relationship to IMP and severity. In addition, TEAEs leading to premature discontinuation of IMP will be summarized and listed. Also, all SAEs, including the non-treatment-emergent SAEs, will be listed.

Counts tables will also be provided for the ISRs and skin events of special interest. Details will be provided in the SAP.

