9. SAFETY REPORTING

9.1. Definitions of Adverse Events, Serious Adverse Events, and Special Situations

9.1.1. Adverse Events

An AE is any untoward medical occurrence, new or worsening of any pre-existing condition, in a clinical study subject administered a medicinal product and which does not necessarily have to have a causal relationship with this treatment.

An AE can therefore be any unfavorable and unintended sign (for example, an abnormal laboratory finding), symptom, or disease temporally associated with the use of a medicinal product, whether or not considered related. AEs may also include pre- or post-treatment complications that occur as a result of CSP-specified procedures, worsening of the targeted disease, overdose, drug abuse/misuse reports, or occupational exposure. Pre-existing conditions that increase in severity or change in nature during or as a consequence of participation in the clinical study will also be considered AEs.

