8.1.7.2. Adverse Events (AEs)

Clinical and laboratory AEs will be coded using the latest version of the Medical Dictionary for Regulatory Activities. System Organ Class (SOC), High Level Group Term, High Level Term, Preferred Term, and Lower-Level Term will be attached to the clinical database.

The following AEs will be considered as TEAEs:

- All events during the complete study, with an onset on or after the IMP start will be counted.

Summaries (number and percentage of subjects and the number of events) of TEAEs by SOC and Preferred Term will be provided by treatment group. Subjects with TEAEs will also be summarized by causal relationship to IMP and severity. In addition, ISRs, skin related AEs, TEAEs leading to premature discontinuation of IMP and SAEs (including the non-treatment-emergent SAEs) will be summarized and listed.

Additionally, selected tables will also be created restricted to events with an onset date on or after the IMP start date and up to 30 days after last dose of IMP.

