Population: safety analysis set.

Table 14.3.1.17: Serious treatment-emergent adverse events: Tabulation for EudraCT reporting

Frequency tabulation per treatment group of serious TEAEs per system organ class and preferred term, showing both the number of subjects and events themselves.

Population: safety analysis set.

Table 14.3.1.18: Non-serious treatment-emergent adverse events: Tabulation for EudraCT reporting

Same as [Table 14.3.1.17](#), but restricted to the non-serious TEAEs.

Population: safety analysis set.

Table 14.3.1.19: Non-serious treatment-emergent adverse events: Tabulation for EudraCT reporting of TEAEs occurring in at least 5% of the overall subjects

Same as [Table 14.3.1.17](#), but restricted to the non-serious TEAEs.

All the lines from the table where there is at least 5% occurrence (of the subjects) of the overall subjects either at system organ class or at preferred term level will be displayed. If the system organ class line is selected but none of the associated preferred terms, then the system organ class will still be presented but without preferred terms.

Population: safety analysis set.

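### The SAP lets a worse causality rating or action taken, on its own, turn a pre-dose AE into a TEAE and split one AE into several events

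*SAP*

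**What the plan says.** SAP 14.1.2 counts as a TEAE any AE that starts between study drug administration and last contact. It adds a clause for AEs already present before dosing that worsen afterwards: "From the worsening, the AE will be considered as a TEAE". Its subsection 14.1.2.1 supplies the meaning of worsening: "A worsening is defined when one of the attributes of the events worsens (severity, seriousness, relationship or action taken"). It then gives the counting rule: "Worsenings observed after first dose of study medication of an event will be considered as a new event, improvements will not". SAP 14.1.6 names the same four attributes when it defines durations, so the list is not a slip.

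Two other places define TEAEs with no worsening clause:
- Protocol 7.3.8.2: "Treatment-emergent adverse events (TEAEs) are defined as those with an onset date/time on or after the start date/time of the first IMP administration".
- SAP 8.1.7.2: "All events during the complete study, with an onset on or after the IMP start will be counted".

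Protocol 9.1.1, which defines an AE and not a TEAE, refers to "Pre-existing conditions that increase in severity or change in nature". It does not mention relationship or action taken.

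Numbers of events are reported as well as numbers of subjects. SAP 8.1.7.2 plans "Summaries (number and percentage of subjects and the number of events) of TEAEs by SOC and Preferred Term will be provided by treatment group". The EudraCT table of serious TEAEs in SAP 14.1.8 is described as "showing both the number of subjects and events themselves", and the non-serious EudraCT tables follow it. SAP 14.1.5 counts a subject once per preferred term and analysis period, at worst intensity, and uses the worst category of a changed attribute in tables.

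**The concern.** Severity and seriousness describe the course of an event. Relationship is a judgement about its cause, and action taken is a response to it. Neither shows that the subject's condition changed after dosing, which is what treatment emergence is meant to capture. A pre-dose AE would normally start with the lowest relationship rating and no study drug action, so a later move in either field is likely to be in the direction that the SAP calls worse.

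The primary endpoint is the incidence and severity of TEAEs, SAEs and AESIs. A rule that moves a pre-dose AE into the TEAE set changes the numerator of that endpoint. It also feeds Figure 14.3.1.1, which shows risk differences against placebo with 95% confidence intervals. The second consequence is narrower: one AE can appear as several events wherever events are counted.

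**Working it through.** The documents give no figure on this point, so there is nothing to reproduce. The check applies the written rules.

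**Inputs**
- Worsening attributes: severity, seriousness, relationship, action taken (SAP 14.1.2.1).
- A pre-dose AE is a TEAE from its worsening (SAP 14.1.2).
- Each post-dose worsening is a new event; improvements are not (SAP 14.1.2.1).
- Planned arm sizes: 40 on MOR106, 20 on placebo (protocol 7.1).

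**Step 1: do the two SAP sections combine?** Section 14.1.2.1 sits under 14.1.2 and contains the only definition of worsening for AEs. Worsening in 14.1.2 therefore takes the four-attribute meaning. A pre-dose AE with constant severity and seriousness qualifies if relationship or action taken alone worsens after dosing.

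**Step 2: event counts.** For k separate post-dose worsenings:
- AE starts after first dose: 1 + k TEAEs.
- AE starts before first dose: k TEAEs.

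Hypothetical AE (assumption): severity and seriousness constant; relationship goes from unlikely to possible; on a later occasion, action taken goes from none to a temporary stop. Here k = 2 under the SAP rule and k = 0 if only severity or seriousness counts.

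| AE starts | SAP rule | Severity/seriousness only |
|---|---|---|
| After first dose | 1 + 2 = 3 | 1 + 0 = 1 |
| Before first dose | 2 | 0 |

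**Step 3: subject incidence.** A promoted pre-dose AE changes overall TEAE incidence only if the subject has no other TEAE. Each such subject then adds:
- MOR106: 1/40 = 2.5 percentage points.
- Placebo: 1/20 = 5.0 percentage points.

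For a single preferred term the condition is weaker: the subject need only have no other TEAE of that term.

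**Step 4: does SAP 14.1.5 undo this?** For splitting after dosing, yes at subject level: the subject is still counted once per preferred term and period. For promotion, no: without the promotion that AE would not be in the TEAE tables at all.

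**Step 5: what is left unspecified.**
- Section 14.1.2.1 makes each worsening a new event, while 14.1.5 takes the worst category for tables. The SAP does not say how these combine in event counts, for example whether an AE that becomes serious is counted in both the serious and the non-serious EudraCT tables.
- The SAP does not say whether relationship is compared on the reported levels or on the two-way split in 14.1.4. On the reported levels, a move from unrelated to unlikely could create a new event although both are classed as not related.

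**Step 6: is the departure logged?** Protocol section 7 asks that deviations be justified in the SAP. The four items that SAP 8.2.1 attributes to the sponsor's decision are legible and do not mention the TEAE definition. The redacted items fall under the early-termination heading and cannot be checked.

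**The case against.** The best defence has five parts.

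**The rule is only for counting.** The title of 14.1.2.1 refers to counting events. If its definition does not govern 14.1.2, however, worsening is undefined for the primary endpoint and still needs wording.

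**Action taken has clinical content.** Protocol 9.1.5 treats study drug interruption, modification or discontinuation as one reason to record an abnormality as an AE. Also, the explicit ALT/AST withholding triggers in protocol 4.5.4 start above 3 x ULN, which is Grade 2 or higher in SAP 14.3.6.2, and subjects above 2 x ULN are excluded at entry. In those cases severity would normally rise too, and either rule would promote the event. This stands, and it narrows the action-taken route mainly to holds that rest on investigator judgement. It does not touch the relationship route.

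**The rule is conservative and the same in both arms.** Over-reporting is not conservative for a comparison. One extra case moves the observed risk difference by +2.5 points if it falls on MOR106 and by -5 points if it falls on placebo.

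**The safety analysis is descriptive and the changes are visible.** SAP section 14 plans no inferential statistics, and Listing 16.2.10.1 shows each change on its own line. This limits the harm, but the tables that report the primary endpoint are still affected.

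**The protocol argument proves too much.** Any worsening clause, even one limited to severity, departs from the onset-only definition. This is right. The objection is to the choice of attributes and to the missing log entry, not to having a worsening clause.

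A reader might also infer that any later update of relationship or action taken triggers the rule. The text does not support that: only worsenings count, improvements are excluded, and nothing says that leaving the not-applicable level for unrelated is a worsening.

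**Conclusion.** The point holds. As written, the SAP can classify a pre-dose AE of unchanged severity and seriousness as a TEAE, contrary to the onset-only definitions in protocol 7.3.8.2 and SAP 8.1.7.2. The effect on overall TEAE incidence is 2.5 points on MOR106 or 5 points on placebo per subject, on the planned arm sizes and only where the promoted event is that subject's sole TEAE. The documents give no frequency for such cases, so neither the total effect nor its direction between arms can be stated.

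It would be tempting to say that multiple counting inflates the primary endpoint. The documents do not support that: splitting an AE after dosing adds to numbers of events in the EudraCT tables and the 8.1.7.2 summaries, and leaves subject counts unchanged. The 1 + k count also assumes worsenings on separate occasions. If several attributes worsen together, 14.1.2.1 need not yield more than one new event. Nor can one say that the change is certainly unlogged, because part of 8.2.1 is redacted.

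**What to change.** 1. In SAP 14.1.2 and 14.1.2.1, limit worsening to an increase in severity grade or a change to serious.
2. Carry relationship and action taken as attributes of the same event at their worst value, as 14.1.5 already does, and state there how the worst-category rule combines with new events in the event-count tables.
3. Align 8.1.7.2 (add the worsening clause) and 14.1.6 (durations) with the same definition.
4. Record the remaining worsening clause in 8.2.1 as a departure from the protocol's onset-only definition, with its reason.

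The cost is SAP wording and a simpler derivation; no new data are needed. The downside is that slightly fewer events are flagged as treatment-emergent. In particular, a pre-dose AE of unchanged severity and seriousness that leads to stopping study drug would leave the TEAE discontinuation table, but Listing 16.2.10.12 is there to show AEs with that action. Listing 16.2.10.1 would still show each change line by line for events that remain TEAEs. Pre-dose AEs that are no longer promoted would appear in Listing 16.2.10.6, which follows the format that shows worst values only; a line per change could be added there if wanted.
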